In order to be able to address future scientific questions, patients will be asked to voluntarily donate biospecimens for banking (please see [section 5.5](#)). If the patient agrees, banked samples may be used for future biomarker research and drug development projects, e.g. to identify patients that are more likely to benefit from a treatment or experience an adverse event (AE), or to gain a mechanistic or genetic understanding of drug effects and thereby better match patients with therapies. As part of this research program, speech sample collection will be done in order to address future scientific questions as described in [section 5.6.1](#).

A separate ocular substudy in selected countries will be conducted. These procedures will be described in detail and implemented via local amendments in the country(ies) planned to participate in this sub-study.

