### 3. DESCRIPTION OF DESIGN AND TRIAL POPULATION

#### 3.1 OVERALL TRIAL DESIGN

The overall trial design is as follows (see Figure 3.1:1):

[figure not shown]

Figure 3.1:1 Trial design

This is a 26-week, multi-center, multi-national, randomized, double-blind, placebo controlled, parallel group trial in patients with schizophrenia. In total, approximately 586 patients with schizophrenia on stable antipsychotic treatment who meet the eligibility criteria are planned to be randomized in equal ratio into this trial.

Patients are enrolled in the trial once informed consent has been signed.

Patients who are deemed eligible by the investigator, after screening, will be randomized to the 26-week treatment period assigned with equal ratio to one of the following arms:

- Icleperkin 10 mg once daily
- Placebo once daily

Randomization of patients will be stratified by MCCB overall composite T-score at screening (screening MCCB overall composite T-score < 30,  $\geq$  30) and participation in the ocular substudy (Yes, No) via Interactive Response Technology (IRT) to balance the baseline cognitive level among groups.

All patients who finish 26 weeks of treatment with Icleperkin or placebo in this study, will be offered the opportunity for treatment with Icleperkin 10 mg in a long-term safety extension trial. Eligible patients may enter the extension trial preferably after completing the EOT visit, or alternatively within 14 days from EoT (i.e. at FU1 visit including the respective time window).

Subjects who do not enroll in the extension study will be followed up for safety for an additional period of 4 weeks after last dose of medication. For further details please refer to [Section 6.2](#). As part of this research program, optional biobanking and speech sample collection will be done in order to address future scientific questions as described in [Section 5.5](#) and [5.6.1](#).

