### 7.2.2 Primary endpoint analyses

The primary analysis of the primary efficacy endpoint uses the Randomized Set. Subjects will be analysed according to the stratum to which they actually belong (not necessarily the stratum they are randomized to, and regardless of any mis-assignment to treatment based on identification of the wrong stratum), as such an error occurs before randomisation and is therefore consistent with the regulatory guidance. Intercurrent events are handled as specified in [Section 7](#) above and missing data as a result from the strategy (including both actual missing outcomes and excluded outcomes) will be handled using a mixed effects model with repeated measures (MMRM) under the assumption of missing at random. For change from baseline to Week 26 in MCCB overall composite T-score, a restricted maximum likelihood (REML) based approach using MMRM will be conducted to compare the adjusted mean between Icleperitin 10mg QD vs. placebo. The MMRM includes the fixed categorical effects of treatment at each visit, fixed categorical effect of the stratification factor using the screening MCCB overall composite T-score, and the fixed continuous covariates of baseline MCCB overall composite T-score at each visit. Subject is treated as random effect. Visit will be treated as the repeated measure with an unstructured covariance structure used to model the within-subject measurements.

The statistical model is:

$$y_{ijkm} = \beta_j S_i + \tau_{jk} + \varphi_m + e_{ij}, \text{ where } e_{ij} \sim N_T(0, \Sigma),$$

where

$y_{ijkm}$  = response variable for subject  $i$  in stratum  $m$  at visit  $j$  receiving treatment  $k$

$S_i$  = the baseline MCCB overall composite T-score of subject  $i$ ,  $i = 1, 2, \dots$

$\beta_j$  = coefficient of baseline effect at visit  $j$ ,  $j = 1, 2, \dots, T$

$\tau_{jk}$  = the effect of treatment  $k$  at visit  $j$ ,  $k = 1, 2$

$\varphi_m$  = the effect of screening MCCB overall composite T-score stratum  $m$  for  $m = 1, 2$ ,  
and  $\varphi_1 \equiv 0$  for stratum 1 of T-score  $< 30$

$e_{ij}$  = the random error associated with  $j$ th visit of the  $i$ th subject.

$\Sigma$  = a  $T \times T$  unstructured covariance matrix

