## 7.4 RANDOMISATION

Eligible subjects will be randomised in equal ratio to Iclepertin 10mg arm and the placebo arm. The randomisation will be implemented in blocks to achieve balanced allocation to each treatment arm. In addition, randomisation will be stratified by two factors: 1) the screening MCCB overall composite T-score (two strata:  $< 30$ ,  $\geq 30$ ) with the cut-off values based on the characteristics of the MCCB overall composite T-score from historical data [[R19-3841](#)], and 2) participation in the ocular substudy (Yes, No).

The randomization will be conducted via an interactive response technology (IRT). BI will arrange for the randomization and the packaging and labelling of trial medication. The randomization list will be generated using a validated system, which involves a pseudorandom number generator so that the resulting treatment will be both reproducible and nonpredictable. The block size will be documented in the CTR. Access to the codes will be controlled and documented.

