7.4 PRIMARY ENDPOINT ANALYSIS

7.4.1 Primary analysis

In the primary analysis under the primary estimand, intercurrent events will be addressed using a strategy that differs depending upon the nature of the intercurrent event. For details please refer to [Section 6.3](#) above (or Section 7 of the CTP). This primary analysis of the primary efficacy endpoint will be performed on the Randomized Set. With regard to the stratification factor, subjects will be analyzed according to the screening MCCB overall composite T-score stratum to which they correctly belong. Missing data resulting from the strategy (including both actual missing outcomes and excluded outcomes) will be handled using a mixed-effects model for repeated measures (MMRM) under the assumption of missing at random.

The primary endpoint is the change from baseline to Week 26 in overall composite T-score of the MCCB.

The primary analysis will be a restricted maximum likelihood (REML) based approach using a mixed-effects model for repeated measurements (MMRM) comparing the change from baseline in MCCB overall composite T-score at Week 26 between icleperitin 10 mg QD and placebo. The MMRM will include the fixed categorical effects of treatment at each visit, a fixed categorical effect of the stratification factor using the screening MCCB overall composite T-score, and a fixed effect for the continuous covariate of baseline (i.e. baseline MCCB overall composite T-score) at each visit. Visit will be treated as the repeated measure with an unstructured covariance structure used to model the within-subject dependencies.

The statistical model will be as follows:

$$y_{ijkm} = \beta_j S_i + \tau_{jk} + \varphi_m + e_{ij},$$

where

$$(e_{i1}, \dots, e_{iJ})' \sim N_J(\mathbf{0}, \Sigma),$$

and

y_{ijkm} = response variable for subject i in stratum m at visit j randomized to treatment k

S_i = the baseline MCCB overall composite T-score of subject i , $i = 1, 2, \dots$

β_j = coefficient of baseline effect at visit j , $j = 1, \dots, J$

τ_{jk} = the effect of treatment k at visit j , $k = 1, 2$

[figure not shown]
φ_m = the effect of screening MCCB overall composite T-score stratum m for $m = 1, 2$,
and $\varphi_1 \equiv 0$ for stratum 1 of T-score < 30

[figure not shown]
e_{ij} = the random error associated with j th visit of the i th subject.

[figure not shown]
Σ = a $J \times J$ unstructured covariance matrix

[figure not shown]

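### Randomisation is stratified by two factors, but the efficacy models adjust for only one; leaving out ocular-substudy participation makes standard errors slightly too large

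*Protocol*

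**What the plan says.** **Randomisation.** Protocol 7.4 states that "randomisation will be stratified by two factors": the screening MCCB overall composite T-score in two strata (<30, ≥30), and ocular-substudy participation. Allocation is 1:1 in blocks. Protocol 3.1 names the same two factors, the second as "participation in the ocular substudy (Yes, No) via Interactive Response Technology (IRT) to balance the baseline cognitive level among groups". Protocol 1.3 adds: "A separate ocular substudy in selected countries will be conducted".

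**Analysis.** Protocol 7.2.2 gives the primary MMRM a "fixed categorical effect of the stratification factor using the screening MCCB overall composite T-score", and the written model has a single stratum term, φ_m, with two levels. SAP 7.4.1 has the same equation and "a fixed categorical effect of the stratification factor using the screening MCCB overall composite T-score". The other readable efficacy models also carry only the MCCB stratum:

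- the MMRM in the protocol synopsis;
- the ANCOVA fitted after multiple imputation (Protocol 7.2.2);
- the MMRM for SCoRS, VRFCAT and PRECIS (Protocol 7.2.3; SAP 7.5.1.1 and 7.5.2);
- the ANCOVA for Tower of London (Protocol 7.2.3; SAP 7.5.2).

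The first two supplementary analyses in Protocol 7.2.2 reuse the primary MMRM. SAP section 4, which lists changes to the planned analysis, does not mention the ocular factor.

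**The concern.** Blocked allocation within strata forces the arms to be balanced on every stratification factor. This reduces the true sampling variance of the treatment difference when the factor predicts outcome. A model that omits the factor leaves its variance in the residual, so the model-based standard error does not reflect that reduction. The interval is then wider than it need be and the test slightly conservative.

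The ocular factor could be prognostic. The substudy runs only in selected countries, and the trial spans about 14 countries and 100 centres (synopsis; Protocol 3.3). Participation is the only part of the randomisation linked to country, and no readable efficacy model contains country, region or site. Raters, test norms and care may differ between countries. The documents neither confirm nor exclude an effect on MCCB change.

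The text does not read like a deliberate choice. SAP 7.4.1 refers to the stratification factor in the singular, and the purpose of stratification given in Protocol 3.1, balancing cognitive level, fits only the MCCB factor.

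**Working it through.** **Inputs from Protocol 7.5:** 220 evaluable patients per arm (440 in total), standardised effect 0.35, one-sided alpha 0.025, stated power 95% (95.6% in Table 7.5: 1), 25% correction for missing data, 586 randomised.

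**Reproducing the plan's figures.** The two-sample t-test (noncentral t, 438 degrees of freedom, noncentrality 0.35 × √(220/2)) gives power 95.57%; the normal approximation gives 95.64%. For sample size, 440/0.75 = 586.7, against 586 stated. The plan's figures reproduce.

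**Inflation by share of variance explained.** Let r² be the share of residual variance explained by the omitted, balanced factor. The reported standard error exceeds the true one by 1/√(1 − r²) − 1. The number of extra patients that would shrink the reported standard error to the correct size is 440/(1 − r²) − 440. The documents do not give r², so a range is assumed.

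| r² (assumed) | SE too large by | Equivalent extra patients |
|---|---|---|
| 1% | 1/√0.99 − 1 = 0.5% | 440/0.99 − 440 ≈ 4 |
| 2% | 1/√0.98 − 1 = 1.0% | 440/0.98 − 440 ≈ 9 |
| 5% | 1/√0.95 − 1 = 2.6% | 440/0.95 − 440 ≈ 23 |

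**Inflation by prevalence and effect.** Let p be the proportion of participants and b the difference in outcome between participants and non-participants, in residual SD. Then reported SE / true SE = √(1 + b²p(1 − p)). Both p and b are assumed. The actual one-sided alpha is 1 − Φ(1.96 × ratio), and power without the term is Φ(0.35√110 − 1.96 × ratio). With the term, power is 95.6% throughout.

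| p | b | SE ratio | One-sided alpha | Power without the term |
|---|---|---|---|---|
| any | 0 | 1.000 | 0.0250 | 95.6% |
| 0.2 | 0.3 | 1.007 | 0.0242 | 95.5% |
| 0.3 | 0.5 | 1.026 | 0.0222 | 95.2% |
| 0.5 | 0.5 | 1.031 | 0.0217 | 95.1% |

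**Simulation.** Stratified permuted blocks were simulated with ANCOVA at n = 440 (20,000 null and 8,000 alternative runs per setting). At p = 0.3, b = 0.5 under the null, the model without the ocular term reported a mean SE of 0.0979 against an empirical SD of 0.0954, with one-sided alpha 0.0222. With the term the figures were 0.0954, 0.0953 and 0.0253. Power was 95.1% without the term and 95.7% with it, in line with the formula.

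**Where power is thinner.** Table 7.5: 1, Scenario #4, assumes an effect of 0.25 for VRFCAT. With 220 per arm and r² = 5%, single-test power falls from 74.4% to about 72.8% at one-sided 0.025. At 0.0125, the level applied to the smaller p-value when the larger one fails, it falls from 64.6% to 62.4%.

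**The case against.** The case for leaving the plan alone is mainly one of size, and most of it is fair.

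- **Direction and size.** The error is conservative, alpha stays at or below 0.025, and primary power moves by at most about 0.6 points over the settings examined. This stands, and it makes the point one of efficiency, not validity.
- **The 5% case is strong.** Solving b²p(1 − p) = 0.05/0.95 gives b = 0.46 SD at p = 0.5 and 0.57 SD at p = 0.2, after adjustment for baseline and MCCB stratum. Both exceed the drug effect of 0.35 SD for which the trial is powered. The 5% row is an upper-end illustration. The figure of 23 patients describes the reported standard error, not lost power, because the estimator already benefits from the stratification.
- **Prognostic value is unproven.** Participation is a patient-level Yes/No, so non-participants may include patients in substudy countries, and baseline adjustment may absorb country differences in level. This stands. If the factor carries nothing, adding it still costs only about one degree of freedom out of several hundred.
- **It may be an operational factor.** SAP 6.4 uses the ocular set for substudy safety, demographic, baseline and ophthalmologic analyses, not efficacy. That could justify omission, but neither document says so.
- **Which stratum value applies.** Protocol 7.2.2 analyses patients by true rather than assigned stratum, which might seem to conflict with using the IRT value. SAP 7.4.1 confines that rule to the screening MCCB stratum, so there is no conflict.
- **Unreadable sections.** The SAP's sensitivity, supplementary and subgroup sections and its SAS code are redacted, and one of them could include the factor. The primary, key secondary and secondary models are readable and do not.

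**Conclusion.** The concern holds. Both documents define two stratification factors or inherit them from the protocol, and every readable efficacy model uses one, without explanation. The consequence is a standard error that is too large if ocular participation is prognostic: 0% to about 3% over p from 0.1 to 0.5 and b from 0 to 0.5 SD. One-sided alpha then lies between about 0.0217 and 0.025. The treatment estimate is not biased and the planned sample size does not change. All sizes rest on assumed values of p, b or r², because the documents give none. The gain from correcting it is small, but it is nearly free and aligns the analysis with the randomisation, so the change should be made.

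**What to change.** Add ocular-substudy participation (Yes/No) as a fixed categorical effect in the MMRM of SAP 7.4.1, in the models of SAP 7.5.1.1 and 7.5.2, and in the ANCOVA fitted after multiple imputation. Align Protocol 7.2.2 and 7.2.3 and the synopsis.

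State that the value is the one recorded in IRT at randomisation. Do not use the flag for the ocular sub-study set: SAP 6.4 lets that set include late or retrospective consent, so membership can be determined after randomisation.

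Make the change before treatment information is released (SAP section 8), since choosing covariates afterwards invites challenge. The sponsor should also decide whether the term carries into the planned three-trial meta-analyses (Protocol 7.2.2). If the factor is left out on purpose, the SAP should give the reason and add a sensitivity analysis that includes it.

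Cost: one term per model, about one degree of freedom and no new data.

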### **7.2.3 Secondary endpoint analyses**

For the two key secondary efficacy endpoints of change from baseline to Week 26 in SCoRS interviewer total score and adjusted total time T-score in VRFCAT, as well as the secondary efficacy endpoint of change from screening to Week 24 in PRECIS total score, the same strategy for handling the intercurrent events in the primary estimand analysis and a similar MMRM analysis used for the primary efficacy endpoint will be conducted to obtain the adjusted mean treatment effect between BI and placebo in terms of change from baseline to Week 26 (from screening to Week 24 for PRECIS total score). This MMRM model includes the discrete fixed effects of treatment at each visit, fixed categorical covariate of the stratification factor using the screening MCCB overall composite T-score, and continuous fixed effects for the corresponding baseline endpoint value at each visit. Visit will be treated as the repeated measure with an unstructured covariance structure to model the within-subject measurements. Subjects will be considered as a random effect. The primary treatment comparison is the contrast between treatments at Week 26 (Week 24 for PRECIS total score). For change from baseline to Week 26 in the T-score of number of correct responses on Tower of London, an analysis of covariance (ANCOVA) model including treatment, stratification factor of screening MCCB overall composite T-score ( $< 30$ ,  $\geq 30$ ), and baseline number of correct responses on Tower of London T-score will be fitted to the data.

Similar sensitivity and supplementary analyses as planned for the primary efficacy endpoint will also be conducted for the two key secondary efficacy endpoints.

## **7.2.5 Safety analyses**

Adverse events will be coded using the Medical Dictionary for Drug Regulatory Activities (MedDRA) coding dictionary. Standard BI summary tables and listings will be produced.

All treated patients will be included in the safety analysis and will be summarized under the actual trial medication received at randomization. In general, safety analyses will be descriptive in nature and will be based on BI standards. No hypothesis testing is planned.

Statistical analysis and reporting of adverse events will concentrate on treatment-emergent adverse events. To this end, all adverse events occurring between the start of treatment and the end of the residual effect period will be considered 'treatment-emergent'. The residual effect period is defined as 12 days after the last dose of trial medication. Adverse events that start before first drug intake and deteriorate under treatment will also be considered as 'treatment-emergent'.

Frequency, severity, and causal relationship of adverse events will be tabulated by system organ class and preferred term after coding according to the current version of the MedDRA.

Frequency tables for all adverse events, protocol-specified adverse event of special interest (AESI), serious adverse event (SAE), adverse event leading to death, adverse event leading to discontinuation, investigator assessed drug-related adverse event and serious related adverse event will be generated for treatment-emergent adverse events. In addition, summary statistics and descriptive analyses will be conducted for other safety parameters that are assessed using dedicated scales, including suicidality as assessed by C-SSRS, disease severity as assessed by PANSS total score and changes over time on AIMS, SAS and BARS scales for EPS and related movement impairments.

Laboratory data will be analysed both quantitatively as well as qualitatively. The latter will be done via comparison of laboratory data to their reference ranges. Values outside the reference range as well as values defined as clinically relevant will be highlighted in the listings. Treatment groups will be compared descriptively with regard to distribution parameters as well as with

regard to frequency and percentage of patients with abnormal values or clinically relevant abnormal values.

Vital signs, physical examinations, or other safety-relevant data observed at screening, baseline, during the course of the trial and at the end-of-trial evaluation will be assessed with regard to possible changes compared to findings before start of treatment.

#### **7.2.6 Other Analyses**

##### **Pharmacokinetic analyses**

Plasma concentrations of Iclepertin at related time points will be analysed descriptively as further explained in [Appendix 10.1](#).

#### **7.2.7 Interim Analyses**

No interim analysis is currently planned but safety will be monitored by an external and independent DMC.

### **7.3 HANDLING OF MISSING DATA**

Every effort will be made to collect complete data at the specific time points, even for subjects who terminated trial medication prematurely. If not specified otherwise, missing data are not imputed and remain missing. Potential outliers will be reported and analysed as observed.

For the primary estimand analysis of the primary efficacy endpoint using the mixed strategy for handling intercurrent events, if a subject misses a visit, the missing data will not be imputed. The MMRM analysis will handle missing data based on a likelihood method under the “missing at random” assumption.

#### **MCCB endpoints**

All imputations will be carried out separately for each study visit since there may be differences in test performance at different time points.

For the domains of Working Memory (consisting Letter-Number Span test and Wechsler Memory Scale 3rd ed. Spatial Span subtest) and the Speed of Processing (consisting Trail Making Test Part A, Brief Assessment of Cognition in Schizophrenia – Symbol Coding subtest, and Category Fluency test – animal naming), if only one of the tests consisting of a domain has missing value at a visit, the corresponding domain score can still be derived using the observed test raw score for that visit. If more than one of the tests consisting of a domain have missing value at a visit, the corresponding domain score is missing at that visit.

For the other five domains (Verbal Learning, Reasoning and Problem Solving, Visual Learning, Attention / Vigilance, and Social Cognition) which has only one test, if the test has missing value at a visit, the corresponding domain score is missing.

If a domain score is missing at a visit, the missing T-score of this domain can be imputed using the proprietary algorithm developed by MATRICS.

For baseline assessment, at least two-thirds of the cognitive domains (i.e., a minimum of five out of the seven domains for the MCCB overall composite score and a minimum of four out of the six domains for the MCCB neurocognitive composite score) need to be successfully assessed at baseline for it to be counted as a test occasion with non-missing baseline value.

For post-baseline assessments, at least half of the domains (i.e., a minimum of four out of the seven domains for the MCCB overall composite score and a minimum of three out of the six domains for the MCCB neurocognitive composite score) need to be successfully assessed to be considered a test occasion with non-missing value.

